Barnardo's will give priority to mainstream foster carers and kinship carers, but will consider extending to short break carers if numbers expressing interest are lower than anticipated. Barnardo's are confident that these carers can be included in the intervention and that WRAP will be suitable. We will seek to recruit a short break carer to better understand their experience of WRAP sessions in our process evaluation if they are included in the sample.

¹⁴ ONS mid-year population estimate for 2020: 127,722 under 18s in H, NL and NEL. This is 1.1% of all under-18s in England. NHS Digital: 3.8% of referrals to CYP's MH services in England in March 2022 were emergency or urgent referrals (3,453). Multiply by 12 months = 41,436. Assume 456 (1.1% of) referrals were from HCC/NL/NEL. Children in foster placements make up 1.02% of the population of under-18s in the three LAs. Looked after children are four times more likely to experience mental health issues than their peers. 1.02% x 4 = 4%, and 4% of 456 is 19. Assume all 19 are in different families.

The evaluation questions and outcome measures will be appropriate for kinship households. We have provided response options in the survey to indicate how each child in the family is related to the carer, including options for foster and kinship care. The theory of change for the intervention was designed with fostering households in mind, but as specified in the intervention protocol WRAP should also be suitable for kinship carers, a point we will explore in the process evaluation.

Sample Size / Minimum Detectable Effect Size Calculations

MDES (Proportion of a Standard Deviation)		0.37 (95% CI 0.11-0.63)
Proportion of variance in outcome explained by covariates ¹⁵ (R ²)	Foster or kinship carer	0.6
	Foster or kinship family	0
	Local authority	0
Intraclass Correlations Coefficient (ICCs)	Foster or kinship carer	n/a
	Foster or kinship family	0.4
	Local authority	n/a
Alpha		0.05
Power		0.8
One-sided or two-sided?		Two-sided
Level of intervention clustering		Household
Average cluster size (if cluster-randomised)		1.9
Expected randomised sample size	Intervention	89 households (167 adults)
	Control	89 households (168 adults)
	Total	178 households (336 adults)
Expected final sample size for analysis	Intervention	62 households (117 adults)
	Control	62 households (117 adults)
	Total	124 households (234 adults)

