We have calculated the Minimum Detectable Effect Size (MDES) as 0.37 for our primary outcome. As shown in the table above, we anticipate 50:50 randomisation of 178 households, or 335 adults. Following dropout etc., we expect an analysable sample of 234 adults in 124 households. We have calculated this with a power of 0.8.

The calculations above assume a 75% response rate to the endline survey as noted in our CONSORT assumption. If we were to have a 65% endline survey response rate (202 adults) the MDES would be 0.40 (0.12-0.68) and for a 55% response rate (172 adults) this would be 0.43 (0.13-0.74).

We have used the following assumptions in our power calculation:

¹⁵ This includes, and will most likely be most influenced by, a baseline measure of the outcome.

- We have used a two-level clustered design to account for household level clustering of adult survey responses. As we are only stratifying for local authority, not randomising at local authority level, we have not used a three-level approach and will instead include local authority as a fixed effect in our models.
- We have assumed an average of 1.9 adults per foster family, including foster carers and other adults in the household. At this ratio, we expect 240 foster carers in 142 foster families. We have assumed a low to moderate ICC of 0.4. We anticipate that scores between adults in the same household will be similar in that households are exposed to some shared risk and protective factors related to wellbeing, such as socioeconomic status. However, wellbeing is subjective and influenced by individual circumstances. Our chosen ICC attempts to address this theoretical basis. Our trial's reported ICCs will be useful to inform power calculations for a future full-scale trial.
- We have assumed a considerable amount of variance as explained by covariates such as a baseline measure of the outcome, as baseline wellbeing scores are likely to be highly correlated with endline scores at an individual level.
- This is our primary outcome and therefore not subject to adjustments for multiple comparisons, so we have used an alpha of 0.05.

The MDES was calculated in R using the PowerUpR package¹⁶. The code used is provided in Annex 2.

Outcome measures

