- Questions referring to **demographics of children** currently in the household. This includes birth, foster, kinship, adoptive, and step children. We will request the child's date of birth and initials to allow data matching.
- A measure of **peer support**: the number of other local foster carers or kinship carers the foster carer could ask for help. The survey will prompt for a numerical answer, and the question will read 'How many other local foster carers or kinship carers could you ask for help if you needed it?'
- A measure of **carer self-reported wellbeing**: the Warwick Edinburgh Mental Wellbeing questionnaire (Tennant *et al.*, 2007). This is a 14-item self-report scale of positively worded wellbeing items and has been validated for use with individuals aged 13 years and above. The psychometric properties of the measure are well-

established, and it has demonstrated sensitivity to change (Collins *et al.*, 2012¹⁷; Maheswaran *et al.*, 2012¹⁸).

- A measure of **carer-reported child wellbeing**: the Brief Assessment Checklist for Children and Adolescents (BAC-A; Tarren-Sweeney, 2013). The BAC-A is a 20-item caregiver-reported measure of mental health difficulties in children and adolescents aged 4-17 years. The measure was developed specifically for children and young people in foster, kinship, and residential care, and children who are adopted. We will ask for a BAC-C or BAC-A (dependent on child age) for every child in the household aged four and above. These outcome measures were developed for use with looked-after children and children with experience of trauma. From our consultations with foster carer advisors, we heard that foster carers see the use of equivalent measures for foster and non-foster children as a positive as foster children are not made to feel different. We have reviewed the items in the BAC-A and BAC-C and none of them seem inappropriate for non-foster children. We anticipate that non-foster children may score differently on these.
- A measure of **carer self-reported family relationships**: the SCORE-15 (Stratton *et al.*, 2010). The Systemic Clinical Outcome and Routine Evaluation-15 (SCORE-15) is a self-report measure of family processes and relationships. While the 15-item version is a relatively new measure, there is evidence to support its psychometric properties.¹⁹

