- dummy variable for gender of foster carer or kinship carer (female, male, neither, unknown);
- dummy variables for ethnic group of foster carer or kinship carer (Asian, Black, Mixed, Other, White, unknown);
- dummy variable for age of foster carer or kinship carer (21-24, 25-34, 35-44, 45-54, 55-64, 65-74, 75-84, 85 and over, unknown);
- dummy variable for whether a single carer or couple (single, partner, unknown);
- deprivation indicator (derived from postcode district);
- baseline WEMWBS score;
- time from randomisation (in months).

If any of the cells defined as above have fewer than 10% of cases, we will merge them with another cell.

We may also include time from first session of intervention in our analysis to explore whether the time between participation and survey completion is associated with outcomes.

Secondary outcomes analysis

Regression models will be used to analyse secondary outcomes. For the majority of outcomes, these will also be linear regression models. We will also run a Poisson regression, and zero-inflated Poisson regression as sensitivity tests in the event that the data contains a substantial number of zeroes. Our approach to reporting on baseline characteristics and adjusting for missing data will be the same as those outlined above. The models used for each secondary outcome are outlined below:

- Carers' perceived peer support: Linear regression (with zero-inflated Poisson regression)
- Mental health of children in household: Linear regression
- Carers' family relationships: Linear regression

For our placement changes outcome, we will analyse this according to our pre-specified reason categories but for robustness will also explore the impact on point estimates and effect sizes when alternative categories are used. For example, we may run a logistic regression where any placement change is included as a placement change regardless of the reason for the change.

The mental health of children will be analysed separately as measured by the BAC and the SDQ. As the SDQ is only available for foster children, this sample size will be smaller i.e. no kinship or birth children. Following What Works for Children's Social Care statistical analysis guidance, our secondary outcomes will be adjusted for multiple tests using the Hochberg's step-up procedure for all secondary analyses.

Other evaluation questions

Exploratory analysis

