We will estimate regression models to analyse the two exploratory outcomes. We will use logistic models given the nature of the data; whether or not a foster/kinship child has been referred to CAMHS since randomisation; and whether or not a foster/kinship carer has ceased fostering since randomisation. We will analyse these outcomes according to our pre-specified reason categories but for robustness will also explore the impact on point estimates and effect sizes when alternative categories are used. Relative risk ratios and percentage point changes will be used to express effect sizes.

We expect that some foster children may move, after randomisation, to a household randomised to a different trial arm. We will report on the proportion of children that move between randomised households, in order to estimate the degree of trial arm 'contamination'.

If data allows we will carry out exploratory analysis with sub-groups or include other variables of interest as predictors in regression analyses e.g. whether facilitator was Barnardo's staff member, or trained carer etc. We intend to include whether adults are foster carers, kinship carers, or other adults in the household, and whether children are birth children, kinship children, and foster children. We will also include time from randomisation in months as an interaction with trial arm (included in main regression model as a fixed effect) in order to explore the relationship of time between baseline and endline surveys with outcome differences between intervention and control groups.

In order to understand how well scores on the Strengths and Difficulties Questionnaire recorded by local authorities and scores on the foster-carer reported Brief Assessment Checklist align, we will use a correlation analysis (Spearman's rho and illustrative plots) to explore this.

Compliance

We will explore the influence of trial arm allocation compliance (i.e. whether individuals in the intervention arm receive WRAP, and how many sessions), by including the number of sessions attended in an instrumental variable analysis. Our compliance analysis will look at carer attendance of at least one WRAP session versus non-attendance in terms of change in the primary outcome at individual carer level.

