Annex 2: Code used to calculate Minimum Detectable Effect Size

```
install.packages("PowerUpR")
library("PowerUpR")

#Primary outcome: Foster carer perceived peer support
#Two-Level Blocked (Fixed) Cluster-level Random Assignment Design
#Level 2 = Family, Level 1 = Adult
#Treatment and randomisation at Level 2

mdes.bcra3f2(power=.80, alpha=.05, two.tailed=TRUE,
             rho2=.4, p=.50, g2=0, r21=0.6, r22=0,
             n=1.9, J=41.3, K=3)
```

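### The secondary models fix no baseline of their own outcome, although four secondary measures are collected at baseline, so precision is given up before the Hochberg correction

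*Protocol*

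**What the plan says.** Under Secondary outcomes analysis the protocol states: "Regression models will be used to analyse secondary outcomes". It then lists a model type per outcome: linear regression for peer support (with a zero-inflated Poisson check), for child mental health ("Mental health of children in household: Linear regression") and for family relationships. No covariate is named for any of them.

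Other parts of the protocol bear on this:

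- The outcome table under Outcome measures ticks both baseline and endline for peer support, BAC, SDQ and SCORE-15. Placement changes are ticked at endline only.
- Under Descriptives, characteristics that are significantly unbalanced between arms will be adjusted for in the outcomes analysis.
- The only baseline score listed as a model covariate is WEMWBS. It is a candidate for the sensitivity models of the primary outcome.
- The sample size section says of the primary outcome: "We have assumed a considerable amount of variance as explained by covariates such as a baseline measure of the outcome".
- The BAC is requested for every child in the household aged four and above, and of the non-foster children the protocol says: "We anticipate that non-foster children may score differently on these". The survey records how each child is related to the carer.
- Under Exploratory analysis, subject to the data allowing it, the team intends to include "whether children are birth children, kinship children, and foster children" as a predictor.

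**The concern.** The baseline value of an outcome is usually its strongest predictor, and adjusting for it narrows the confidence interval of the treatment effect whether or not the arms happen to differ at baseline. A rule that admits a covariate only when the arms differ significantly selects on chance imbalance rather than prognostic strength. Under randomisation it will usually leave the baseline out. The protocol pays to collect four secondary baselines, recognises in its power calculation what a baseline is worth, and then fixes no use of these baselines as covariates. The cost is wider intervals in four of the five secondary comparisons, which also face a multiplicity correction. Since the pilot is meant to inform a full-scale trial, less precise secondary estimates also make it less informative for planning.

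**Working it through.** **Inputs.** Annex 2 gives the code "mdes.bcra3f2(power=.80, alpha=.05, two.tailed=TRUE" with "rho2=.4, p=.50, g2=0, r21=0.6, r22=0", 1.9 adults per household and 41.3 households in each of 3 local authorities (123.9 households). The protocol states no power, ICC or R² for any secondary outcome. Using these primary inputs for a carer-level secondary outcome (peer support, SCORE-15) is therefore an assumption.

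**Formula.** Var = ICC(1 − R²_family)/(0.25 × 123.9) + (1 − ICC)(1 − R²_individual)/(0.25 × 123.9 × 1.9). MDES = (t for alpha + t for power) × √Var, with 3 × (41.3 − 2) = 117.9 degrees of freedom. Power is from the noncentral t.

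**Reproducing the plan's figure.** With R² 0.6 at individual level and 0 at family level, Var = 0.01291 + 0.00408 = 0.01699 and SE = 0.1304. The multiplier is 1.980 + 0.845 = 2.825, so MDES = 0.368, which matches the stated 0.37. The stated 0.40 at 202 adults and 0.43 at 172 adults also reproduce (0.398 and 0.432).

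**Without a baseline.** With R² = 0, Var = 0.01291 + 0.01019 = 0.02311 (rounded components) and SE = 0.152. MDES rises to 0.43. The variance is 0.02311/0.01699 = 1.36 times that with R² 0.6.

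**Power at 0.37 SD**, with the R² values as an assumed range:

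| R² individual / family | SE | Power at 0.05 | Power at 0.01 |
|---|---|---|---|
| 0 / 0 | 0.152 | 67.5% | 43% |
| 0.25 / 0 | 0.143 | 73% | 49% |
| 0.36 / 0 | 0.139 | 75% | 52% |
| 0.49 / 0 | 0.135 | 78% | 55% |
| 0.6 / 0 (protocol's structure) | 0.130 | 80% | 59% |
| 0.25 / 0.25 | 0.132 | 80% | 58% |
| 0.49 / 0.49 | 0.109 | 92% | 78% |

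The 0.01 column is the strictest Hochberg step, 0.05/5, counting BAC and SDQ separately alongside peer support, SCORE-15 and placement changes.

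**Child outcome.** Assume an ICC of 0.4, the same 123.9 households and (544 + 59)/178 = 3.39 children each. The MDES at 0.05 is 0.386 without a baseline and 0.348 with individual-level R² 0.6.

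**Child type (BAC only).** The share of variance explained is p(1 − p)D²/(1 + p(1 − p)D²), where p is the birth-child share and D the score difference in SD. The summary table's counts give p = 59/603 = 9.8%. With 1.88 foster children per family (178 × 1.88 ≈ 335), p = 59/394 = 15%. For an assumed D of 0.5 to 1, the term explains 2% to 11% of variance. That takes about 1% (p 9.8%, D 0.5) to 6% (p 15%, D 1) off the SE. Kinship numbers are unknown and not included.

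**The case against.** The strongest reply is that the protocol is silent rather than wrong. It names a model type, does not exclude a baseline, and a statistical analysis plan not shown here may list covariates. The rule restricting predictors to unbalanced ones is written for the primary model. This stands in part: it would be wrong to say that secondary baselines are ruled out. But the protocol does state one general rule for bringing covariates into the outcomes analysis, and that rule is a significance test of imbalance. As written, the baselines would normally stay out.

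A reader might also infer more than the documents support:

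- *That the secondary comparisons are biased, or that an uneven mix of child types passes unchecked into the BAC effect.* Randomisation makes the unadjusted comparison valid. Chance imbalance adds variance, not bias, and a significant imbalance would trigger the adjustment rule.
- *That child type is absent from the plan.* It is an intended exploratory predictor. Pooling of child types concerns the BAC only: the SDQ covers foster children, and peer support and SCORE-15 are carer-level.
- *That adjustment would lift power to 80% to 92% at R² of only 0.25 to 0.49.* That needs the baseline to explain variance between households as well as within them, whereas the protocol's own inputs set family-level R² to 0.
- *That the local authority term is missing.* The sample size section already places it in the models.

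There are practical limits too. The baseline survey is sent after randomisation, children move between households, and the SDQ informant is generally unknown. These shape how adjustment is done and reduce its yield, but they do not argue for leaving it to an imbalance test.

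**Conclusion.** The point holds as a loss of precision, not of validity. For a carer-level secondary outcome with the protocol's primary design inputs, omitting the baseline costs about 5 to 13 percentage points of power at 0.37 SD (67.5% against 73% to 80%). At the strictest Hochberg step it costs about 6 to 16 points (43% against 49% to 59%). The gain would be larger if baselines also explained between-household variance. These sizes rest on borrowing the ICC of 0.4 and the sample size from the primary outcome, and on an assumed individual-level R² of 0.25 to 0.6.

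Nearly all of the gain comes from the baselines. Child type in the BAC model is a minor addition, partly overlapping with baseline BAC. The point does not extend to placement changes. It merits a change because the data are already being collected.

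**What to change.** In the main models for peer support, BAC, SDQ and SCORE-15, pre-specify the outcome's own baseline score as a covariate regardless of any imbalance test, with local authority as already planned. Specify which baseline counts: survey responses completed before WRAP starts, and for the SDQ the score held at randomisation (Annex 3). Keep participants and children without a baseline in the analysis through the covariate imputation already planned. For the BAC only, move child type (foster, kinship, birth) from the exploratory analysis to the main model.

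The change is one of wording and needs no new data. It costs a few degrees of freedom. Baselines will be missing or less reliable for children who join a household later or whose SDQ informant is unknown, so the gain for the child outcomes may be smaller than for the carer outcomes.
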